The couples will be recruited from the list of women who are receiving BISP-CT and meet the eligibility criteria of: adult married women who: receive BISP-CT, have one child of at least 18 months and have no family migration plan for next 2 years.

The couple in which either of the partners has gross mental impairment, physically challenged or bedridden, will be excluded.

Sample Size

There will be three groups for cRCT. The first group will receive LSB to BISP-CT beneficiaries and their husbands. The second group will receive LSB only to women receiving BISP-CT. The third group will be the control arm who will receive BISP-CT only. Assuming an average cluster size of at least 25 couples, with the baseline prevalence of depression 60% and expected reduction of 20% in intervention arm, 9 clusters per arm would be needed over a period of two years. There are three arms and 9 clusters in each arm so a total of 675 couples (225 in each arm, 25 in each cluster). By accounting for the attrition rate of 25%, a minimal of 846 couples (282 per arm) would be needed.

Sampling Strategy

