During the first level of assessment, out of the four Tehsils in District Thatta, Tehsil Mirpur Sakro will be finalized for the intervention, since Tehsil Thatta is saturated with other NGOs/Projects, Tehsil Ghorabari and Tehsil Ketu Bunder are difficult to manage administratively, being far away and coastal areas. At the second level of assessment in Tehsil Mirpur Sakro, the UCs will be assessed based on the demographic characteristics, infrastructure, health facilities, accessibility and women mobility. The UCs being administratively hard to reach i.e. lack proper infrastructure (roads), saturated with other projects, being close to city with urban settlements, will be excluded. Three UCs i.e. Gharo, Gujjo and Chowbandi will be identified as the potential sites for the intervention. Within the UCs, Deh/Village is the smallest unit, but since there is no clear demarcation between Dehs, therefore village or a group of small villages will be considered as a cluster. The clusters will be created by grouping small villages with respect to geographic boundaries, ethnic cast and number of households. Each cluster will have sufficient number of households to achieve the targeted cluster size. The large geographically separated villages will be considered independent clusters. The mapping of clusters will be done in a way to maximally avoid contamination. A minimum of 27 clusters will be selected randomly from a sufficient pool of clusters i.e. 9 from each arm keeping same number of clusters per arm in each UC. At the third level of assessment, the clusters of the selected UCs will be randomly assigned to three arms. The clusters will be selected for randomization based on the assumptions, i.e. having sufficient number of BISP beneficiary households meeting our eligibility criteria, the intervention and control clusters will not be in close proximity thus chances of contamination are minimal.

Operational Plan

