To avoid possible human error of missed or incorrect entries, the entered data will be cross checked initially by data coordinator, and discussed with research team and principal investigators, if required. All the data will be double entered in Excel, followed by congruence check and cleaning. It will be imported to STATA version 12.1 for the analysis, after cleaning.

Descriptive Statistics: Descriptive statistical analysis will be run to look at the distribution of variables of interest and for outcome variables. Mean and standard deviation will be calculated for continuous variables, proportions will be calculated for the categorical variables.

Logistic regression will be used to assess the effect of LSB with maternal depression and other outcomes. All variables meeting the criteria will be used for building the final model. The variable found most significant in the univariate analysis will be subsequently added first and the next significant variable one after the other. Variables found statistically non-significant (>0.05), biologically not meaningful will be removed from the model. Multivariate logistic regression will be carried out to reach to the most parsimonious model.

Communication Plan and Stakeholder Management

The project team will involve stakeholders at multiple levels. At national, coordination with BISP office in Islamabad and other relevant programs on maternal and child health will be carried out to sensitize them about the study scope and the outcomes and their implications on policy. Study team will meet regularly in coordination with Umeed-e-Nau program management over the study period and will discuss the project implementation.

Local stakeholders will include the BISP offices in Sindh province. Regular coordination is needed with the provincial office Local Health Department in the study will also be presented the results. Biannual meetings will be set with local stakeholders to share research progress and milestones.

Monitoring and Evaluation Plan

The primary responsibility for monitoring the fidelity of the intervention delivery will rest with Aga Khan University and they will be required to ensure that a log sheet is kept recording the trainings conducted by faculty of AKU to train LSB teachers and number of couples who attended the training. This information will be reported quarterly to Principal Investigators. The information

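### Village clusters are randomised, but the only inferential analysis stated is logistic regression with no allowance for clustering, so p-values and confidence intervals would be too optimistic.

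*Protocol*

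**What the plan says.** The design is clustered throughout the protocol. Under Sampling Strategy, a "village or a group of small villages will be considered as a cluster", and "the clusters of the selected UCs will be randomly assigned to three arms". The same section restricts the allocation: "9 from each arm keeping same number of clusters per arm in each UC", with three UCs named as potential sites. The Sample Size section counts in clusters: "Assuming an average cluster size of at least 25 couples", it concludes that "9 clusters per arm would be needed over a period of two years", which is 225 couples per arm before attrition and 282 after.

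The Data Analysis section of the trial phase gives descriptive statistics and then one inferential method: "Logistic regression will be used to assess the effect of LSB with maternal depression and other outcomes". It goes on to say how the model is built. Variables enter in order of univariate significance, those with p above 0.05 are removed, and a multivariable logistic model is reduced to its most parsimonious form. Neither this section nor any other mentions a random effect, GEE, cluster-robust standard errors, cluster-level summaries, an ICC or a design effect.

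**The concern.** When whole villages are allocated, women in the same village share influences on the outcome and do not contribute independent information. Here the protocol itself gives reasons to expect this. Sampling Strategy groups small villages by geography, ethnic or caste affiliation and household numbers, so members of a cluster are alike by construction. The training is delivered in groups by 12 teachers (Key Intervention; Operational Plan), which adds shared group and teacher effects in the intervention arms.

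Logistic regression on individual records without a cluster term computes its standard error as if every woman were independent. Any positive ICC then makes the standard error too small, the confidence interval too narrow and the p-value too low. The sentence covers depression, which drives the sample size, and other outcomes as well. The protocol looks to the trial to support scale-up across Pakistan, so a false-positive result would be costly.

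**Working it through.** **Inputs from the protocol.** 9 clusters per arm; 25 couples per cluster (m = 25), or 282/9 = 31.3 as enrolled; outcome prevalence 60%.

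**Inputs not stated, assumed here.** Two-sided alpha 0.05; ICC from 0.01 to 0.10.

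**1. Can the ICC be recovered from the stated sample size?** Not uniquely, because alpha, power and ICC are all absent and the 20% reduction may be absolute or relative.

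- Absolute reading, 60% v 40%, 80% power, pooled two-proportion formula: n = [1.96·√(2·0.5·0.5) + 0.842·√(0.6·0.4 + 0.4·0.6)]² / 0.20² = 97 per arm. The stated 225 then allows a design effect of 225/97 = 2.32, so ICC = (2.32 − 1)/24 = 0.055.
- Same reading, 90% power: n = 130, design effect 225/130 = 1.73, ICC = 0.030.
- Relative reading, 60% v 48%, 80% power: 270 per arm are needed even at ICC 0, so 225 leaves no room for any positive ICC.

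**2. Effect of ignoring clusters.** Design effect DE = 1 + (m − 1)·ICC. The naive standard error is too small by a factor √DE. The true type I error of a nominal 5% test is 2·[1 − Φ(1.96/√DE)]. For example, at ICC 0.05, DE = 1 + 24·0.05 = 2.20, √DE = 1.48, 1.96/1.48 = 1.32, and the type I error is 18.6%.

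| ICC | DE (m = 25) | SE too small by factor | Type I error, formula | Type I error, simulated, m = 25 | Simulated, m = 31 |
|---|---|---|---|---|---|
| 0.01 | 1.24 | 1.11 | 7.8% | 7.8% | 8.8% |
| 0.02 | 1.48 | 1.22 | 10.7% | 10.8% | 12.4% |
| 0.03 | 1.72 | 1.31 | 13.5% | 13.7% | 15.6% |
| 0.05 | 2.20 | 1.48 | 18.6% | 18.8% | 21.6% |
| 0.10 | 3.40 | 1.84 | 28.8% | 28.9% | 33.0% |

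The simulations are beta-binomial under the null: 9 v 9 clusters, prevalence 60%, 40,000 runs, Wald test from unadjusted individual-level logistic regression. At ICC 0 the same test gave 4.9% (m = 25) and 5.1% (m = 31), so the excess comes from clustering alone. At the ICCs implied by the absolute reading, 0.030 and 0.055, the formula gives about 14% and 20%.

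**3. Does a cluster-based analysis cure it?** In the same simulated data, a t-test on the 9 v 9 cluster proportions rejected in 4.9% to 5.3% of runs at every ICC from 0 to 0.10.

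**4. Allowing for balance by UC.** The table treats all clusters as exchangeable. A further simulation placed three clusters per arm in each of three UCs (9/3 = 3), with m = 25, and put an assumed share of the between-cluster variance between UCs.

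| Total ICC | 0% between UCs | 25% | 50% |
|---|---|---|---|
| 0.02 | 11% | 9% | 8% |
| 0.05 | 19% | 16% | 12% |

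**The case against.** The strongest objection is that the protocol says only logistic regression. A random-intercept model, or a logistic model with cluster-robust errors, also goes by that name, and the authors clearly knew the trial was clustered because they sized it in clusters. On this view the variance method is merely unstated and may sit in an analysis plan that is not shown. It is true that the words ordinary and individual-level are an interpretation. But the section is not a bare outline. It fixes the software, the order of variable entry, the removal threshold and the form of the final model, and what it describes is standard covariate selection on individual records. An analyst following it would not account for village.

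Other points partly stand:

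- The inflation depends on an ICC the protocol does not give, and at ICC 0.01 it is modest, about 8%.
- The ICC of 0.055 rests on an absolute reduction, 80% power and a two-sided 5% test. Other readings give 0.030 or no positive value.
- Balance by UC removes between-UC variation from the arm comparison, so the exchangeable-cluster rates are upper figures unless the ICC is read as within-UC.
- Leaving out a UC term does not make standard errors too small. It tends to work in the conservative direction, so it is a secondary point.
- The sentence says other outcomes, not all outcomes. Several instruments yield scores (self-efficacy 10–40, resilience 14–98, gender attitudes 21–84), and the section does not say how each is modelled.

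None of these restores a 5% error rate for a logistic analysis without clustering, unless the ICC within UC is zero.

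**Conclusion.** The concern holds. The stated analysis does not match the unit of randomisation. Followed as written, it gives confidence intervals that are too narrow and p-values that are too small for depression and for any other outcome analysed the same way.

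For 9 v 9 clusters of 25 and an assumed ICC of 0.01 to 0.10, true type I error is about 8% to 29% against a nominal 5%. With the enrolled cluster size of about 31 it is about 9% to 33%. If a quarter to a half of the between-village variance lies between UCs, the figures are about 8% to 9% at a total ICC of 0.02 and 12% to 16% at 0.05. The ICC range and the UC shares are assumptions; the direction of the error is not. This must be fixed before analysis.

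**What to change.** Replace the logistic regression sentence in Data Analysis with one that names the clustering method:

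- For binary outcomes, use mixed-effects logistic regression with a random intercept for cluster, or GEE with a small-sample variance correction, or a t-test on cluster-level summaries. Use the corresponding clustered model for any outcome analysed as a score.
- Include UC as a fixed effect, because allocation is balanced within UC.
- Base degrees of freedom on clusters: 18 − 2 = 16 for a comparison of two arms, and 14 after adjusting for three UCs.
- Keep the arm term in every model, so that it cannot be dropped by the variable-removal rule.
- State the assumed ICC with the sample size, and report the estimated ICC with the results.

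The cost is a change of wording and of model command, with no new data or participants, and intervals that are correctly wider. Power under a valid analysis depends on what the 20% reduction means. With 225 per arm at ICC 0.05 (normal approximation) it is about 82% for 60% v 40%, but about 41% for 60% v 48%, where it is only about 73% even at ICC 0. That reflects the ambiguity in the sample size, not a cost of the corrected analysis.

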The aim of this research is in line with the 2030 agenda for Sustainable Development Goals. This agenda is a plan of action to strengthen universal peace and recognizes poverty as the greatest hurdle in sustainable development. The first goal of this document is concerned with a step of reducing poverty and the second goal aims to bring the efforts for gender equality by empowering women. Through BISP-CT intervention, it is hoped that the overall economic wellbeing of the women and their families will improve and through LSB, women will become more empowered. Ultimately they will be able to compete in the world as global citizen alongside men (Agenda for Sustainable Development, 2030). This study aims to engage men in women empowerment (MEWE) through LSB and BISP-CT to improve maternal mental health in Pakistan using a randomized control trial.

Primary Objectives

To measure the impact of men engagement in LSB and CT on maternal depression, domestic violence, improved self-efficacy and women empowerment.

Secondary Objectives

To measure the impact of men engagement in LSB and CT on Household food security, Gender Attitude, Economic Solvency and Resilience.

Primary Outcomes

Reduced maternal depression, domestic violence, improved self-efficacy and women empowerment.

Secondary Outcomes

Improved household food security, gender attitude, economic solvency and resilience.

Method

Program Implementation and Approach

The proposed study areas for the Formative Phase of the project are Punjab (Rahimyar Khan), Balochistan (Lasbela), Khyber Pukhtunkhuwa (Peshawar) and Sindh (Thatta). The cRCT will be conducted in district Thatta.

Key Intervention

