The outcomes will be assessed through validated instruments including Patient Health Questionnaire (PHQ-9), The Revised Conflict Tactics Scale, General Self-Efficacy Scale, Resilience Scale, Economic Solvency, Gender Equitable Attitude Scale and Six-item Food Security Questionnaire. Pilot testing will be done followed by modifications in the tools, if and where required.

Demography

Demographic profile will be used to assess the overall information about the family, its economic and educational status. This form was designed and utilized in the Global Network Research Unit (GNRU) project on perinatal infections and pregnancy outcomes which was funded by National Institute of Health (NIH), with AKU and University of Alabama as partners and other AKU funded researches (Karamaliani et al., 2009). This demographic profile form includes two sections:

Section A: Demographic profile: age, education, language, number of family members, number of married or unmarried and previous pregnancies and number of children.

Section B: Socio-economic Status: number of people actively working including type of work, timings and utilization, type of living with accessories and water drinking.

Section C: Economic Solvency: Financial assistance received other than BISP, financial assistance received for child support and cash assistance received from other people.

General Self-Efficacy Scale (GSE-10)

This 10-item instrument was created to assess a general sense of perceived self-efficacy with the aim to predict coping and adaptation after stressful life events (Schwarzer, 1995). Responses to each item are made on a 4-point scale: 1=Not at all true, 2=Hardly true, 3=moderately true, 4=exactly true. The possible range of scores is 10 to 40. In samples from 23 countries, Cronbach's alphas ranged from 0.76 to 0.90, with the majority in the high 0.80s. For the GSE, the total score ranges between 10 and 40, with a higher score indicating more self-efficacy (Schwarzer, 1995). For this study, the Urdu adaptation of the GSE tool, developed by Tabassum, Rehman, Schwarzer, and Jerusalem was used (Tabassum et al., 2003).

The Revised Conflict Tactics Scale (CTS2S-20)

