We will use Wagnild's resilience scale for our study. This tool has been validated in Urdu in Pakistani context. This resilience scale comprised of five core characteristics of resilience that include: purposeful life, perseverance, equanimity, self-reliance and existential loneliness. It comprised of validated 14 items with 7-point Likert scale to rate the individual's evaluation ranging from 1 (Strongly Disagree) to 7 (Strongly Agree) (Shehzad et al. 2015). Item scores are summed to yield a total score ranging from 14 to 98, with higher scores suggestive of greater perceived resilience categorized as very low (14-56), low (57-64), on the low end (65-73), moderate (74-81), moderately high (82-90), and high (91-98).

Gender Equitable Attitude Scale (GEAS-21)

The Gender Equitable Attitude Scale is a 21 item scale with Likert scale ranging from 4 (strongly agree) to 1 (strongly disagree). It has been adapted from 34-item original "The Gender-Equitable Men Scale (GEM Scale)" and 13-item "Gender Equitable Men Scale" adapted in the context of Pakistan. This scale has been tested by Pak-IMAGES study by Promundo and Men's HUMQADAM program by Rozan (Ashfaq et al., 2018). Factor analyses support two subscales, and the scale is internally consistent ($\alpha = .81$) (Pulerwitz & Barker, 2008). The total score ranges from 21-84, where higher score shows more gender equitable attitudes.

Six-item Food Security Questionnaire (FSQ-6)

A six-item food security questionnaire (FSQ) will be used to assess the food insecurity. The scale is valid, reliable and sensitive screening tool of food insecurity in people. One study had found that a strong correlation between the two-item and six-item FSQ ($\rho: 0.895$; 95% CI 0.821, 0.940; $P, 0 < 0001$). Cronbach's α coefficient was found to be 0.94 and 0.90 for the two-item and six-item FSQ, respectively. FSQ yielded a sensitivity of 100% (95% CI 75, 100) and a specificity of 78% (95% CI 61, 90). The negative predictive value was found to be 100% (95% CI 88, 100) (Young, et.al 2009). The total score ranges between 0-6, where score 0-1 shows high or marginal food security, score 2-4 shows low food security, score 5-6 shows very low food security.

Data Analysis

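### Logistic regression is the only effect model named, but self-efficacy (primary) and gender attitude (secondary) are defined only as total scores, with no event or cut-point

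*Protocol*

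**What the plan says.** The Data Analysis section that follows Assessment Tools names one effect model: "Logistic regression will be used to assess the effect of LSB with maternal depression and other outcomes". The final adjusted model is logistic again. Continuous variables appear only under Descriptive Statistics: "Mean and standard deviation will be calculated for continuous variables, proportions will be calculated for the categorical variables".

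The primary outcomes are "Reduced maternal depression, domestic violence, improved self-efficacy and women empowerment" and the secondary outcomes are "Improved household food security, gender attitude, economic solvency and resilience". Assessment Tools defines two of these only by a range and a direction:

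- Self-efficacy (primary): "For the GSE, the total score ranges between 10 and 40, with a higher score indicating more self-efficacy".
- Gender attitude (secondary): "The total score ranges from 21-84, where higher score shows more gender equitable attitudes".

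Neither scale has a band, cut-point or event.

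Covariates are entered by univariate significance: "The variable found most significant in the univariate analysis will be subsequently added first and the next significant variable one after the other". They are removed by the same criterion: "Variables found statistically non-significant (>0.05), biologically not meaningful will be removed from the model". Nothing is exempted from this rule, although the Operational Plan measures the outcomes at baseline and at five months, and Tracking Participants describes a closed cohort.

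**The concern.** A binary logistic model needs an event, and the protocol supplies none for these two scales. An analyst who follows the stated method in its ordinary form must pick a threshold on a 10 to 40 or 21 to 84 score. That choice would be made after the protocol, possibly with data in view, and the result would depend on where the cut falls. A split also treats everyone on one side of the cut as equal, which wastes information in a trial with only 9 clusters per arm. One of the four primary outcomes is affected.

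A smaller issue sits in the same section. Under the significance-based rule, whether the baseline value of an outcome is in the model depends on the data and can differ between outcomes.

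**Working it through.** **The mismatch.** This part needs no arithmetic. The scales in Assessment Tools compare as follows:

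| Scale | Outcome | Score | Cut-points or bands given |
|---|---|---|---|
| GSE-10 | self-efficacy, primary | 10 to 40 | none |
| GEAS-21 | gender attitude, secondary | 21 to 84 | none |
| PHQ-9 | depression, primary | 0 to 27 | 5, 10, 15, 20 |
| RS-14 | resilience, secondary | 14 to 98 | six bands |
| FSQ-6 | food security, secondary | 0 to 6 | three bands |

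For the first two rows the protocol gives nothing from which a binary event could be built.

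**What a split would cost (illustration).** From the protocol's Sample Size section: 9 clusters of 25, so 9 × 25 = 225 per arm. Assumed here, because the protocol states none of them: a normally distributed score, ICC of 0.02, 0.05 or 0.10, the location of the split, and a true difference of 0.4 SD. The protocol gives no power for these scales, so there is no figure of its own to reproduce.

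1. Efficiency of a split at quantile p, ignoring clusters: φ(z)² / [p(1−p)]. At the median this is 2/π = 0.637; at the 80th percentile it is 0.490.
2. A split also lowers the ICC. At the median the binary ICC is (2/π)·asin(ICC) = 0.0127, 0.0318 and 0.0638.
3. Design effect of the score: 1 + 24 × ICC = 1.48, 2.20 and 3.40. Design effect of the median split: 1 + 24 × binary ICC = 1.31, 1.76 and 2.53.
4. Information retained = efficiency × (design effect of score / design effect of split). At ICC 0.05: 0.637 × 2.20 / 1.764 = 0.794.
5. An ordinal model on the total is approximated by ranks: 3/π, with rank ICC (6/π)·asin(ICC/2).
6. Difference detectable with 80% power = (t₀.₉₇₅ + t₀.₈₀) × √(2 × design effect / 225 / retained), on 16 df, where the two t values sum to 2.985. For the score at ICC 0.05: 2.985 × √(2 × 2.20 / 225) = 0.417 SD.

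| | ICC 0.02 | ICC 0.05 | ICC 0.10 |
|---|---|---|---|
| Retained, median split | 0.722 | 0.794 | 0.855 |
| Equivalent clusters per arm (9 × retained) | 6.5 | 7.1 | 7.7 |
| Retained, ordinal | 0.969 | 0.979 | 0.986 |
| Detectable difference, score (SD) | 0.342 | 0.417 | 0.519 |
| Detectable difference, median split (SD) | 0.403 | 0.468 | 0.561 |

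7. Simulated power for a true 0.4 SD at ICC 0.05 (20,000 trials, t-test on cluster means): about 77% on the score, 76% on ranks and 67% with a median split. A split at the 80th percentile gives about 59% if the cut is taken from both arms pooled, and about 62 to 64% if it is taken from the control arm. Even that small choice moves the answer.

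**Baseline value.** With n = 3 × 225 = 675 and baseline correlation r, the univariate statistic is t = r√(673/(1−r²)). At r = 0.4 it is 11.3, or 6.1 after division by √3.4 for clustering at ICC 0.10, so the baseline value would almost always be selected if it is a candidate. At r = 0.1 it is 2.6 or 1.4, and selection happens in roughly 74% or 29% of trials. At such a weak correlation, adjustment hardly matters.

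**The case against.** The strongest reply is that the section says logistic, not binary. An ordinal logistic model on the total is a logistic regression, needs no threshold and costs 1 to 3%. A reader might infer that a primary outcome is left without any model that fits it; the text does not support that, because the ordinal reading is open. What stands is that no ordinal model is named, so the form has to be guessed. Improved versus not improved since baseline is another possible event, but the protocol does not define it either.

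A second reply is that cut-points and model forms often belong to a statistical analysis plan. That covers silence. Here the protocol has fixed a model, and a later plan would have to depart from it or add a threshold or an ordinal form that the protocol lacks.

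Third, the losses are hypothetical. The protocol proposes no split, and the ICC, normality and effect size are assumed. This is correct. A cruder calculation that applies the score's design effect to the split as well gives 82% against 62% at ICC 0.05 and 0.4 SD. That gap is too wide, because a split also reduces the ICC, and it is not relied on here.

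Fourth, resilience and food security have bands but no named event, and PHQ-9 and the Conflict Tactics Scale offer several scorings. That is fair, but those scales at least state categories or scoring options, and depression was sized as a prevalence. The point is kept to the two scales with none.

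Finally, a reader might infer that the selection rule costs precision by dropping the baseline value. The check above does not support that.

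**Conclusion.** The point holds for GSE-10 and GEAS-21: the only effect model named, read in its ordinary binary form, needs an event that the protocol does not define. This conclusion rests on the text alone.

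The size is conditional. If a median split were chosen, about 14 to 28% of the information would be lost over ICC 0.10 to 0.02, and power for 0.4 SD at ICC 0.05 would be about 10 percentage points lower. These figures assume a normal score and 9 clusters of 25 per arm. They do not show that this trial will lose that much, nor that any power stated for these scales is missed.

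The baseline point is secondary. Its benefit is the same pre-specified adjustment for every outcome, with no gain in precision claimed.

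**What to change.** In Data Analysis, state that end-line GSE-10 and GEAS-21 totals are analysed with a linear mixed or cluster-level model that accounts for the randomised clusters. A named ordinal logistic model with clusters would also close the gap at little cost. Keep logistic regression for outcomes given a binary definition, such as depression prevalence.

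In the same paragraph, state that arm and the baseline value of the same outcome are always in the model and are exempt from significance-based entry and removal.

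The cost is a wording change made before end-line data are seen. No new instrument, visit or participant is needed, because both assessments are already planned. A small downside is that mean differences are less familiar to policy readers than prevalences.
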